## **Ethical considerations**

This study was submitted to the HCPA Ethics and Research Committee, which assessed all aspects necessary for the proper conduct of the study.

## **Property of informations**

Both patients' privacy and confidentiality will be preserved. Only general data will be released.

## SCHEDULE

If the CEP/HCPA is approved, it is expected to start activities in June 2016.

PHASES	Period
CEP appreciation / approval	May/2016
Data collect	June/2018-November/2021
Literature review	May/2017-March/2021
Data analysis and interpretation	December/2021
Writing for National Congress	December/2021
Submission of the article for submission to an indexed journal	December/2021

## BUDGET

Funds will be requested from funding agencies (FAPERGS, CNPq, PROPESQ, FIPE).

Item	Value in Reais (R\$)
Typing and article formatting	100,00
Spell check	120,00
Paper sheets (size: A4)	15,00
Printer ink	40,00
Total	275,00

MISOPROSTOL-200 PROJECT PROTOCOL 16-0309

Paste patient label on here

Patient's name: \_\_\_\_\_ Age: \_\_\_\_\_

Hospital Registration: \_\_\_\_\_ Telephone: \_\_\_\_\_

Date of admission: \_\_\_\_\_ / \_\_\_\_\_ / \_\_\_\_\_ Discharge date: \_\_\_\_\_ / \_\_\_\_\_ / \_\_\_\_\_

**White ( ) Black ( ) Brazilian Indian ( ) Asian ( )**

**Gesta:** **Para:** **Miscarriage:**

Approximate gestational age : \_\_\_\_\_

## Inclusion criteria

Has indication for uterine evacuation	Yes(  )	No(  )
GESTATION < 12 WEEKS	Yes(  )	No(  )

Any **NO** excludes

### **Exclusion Criteria (Yes):**

Do you have any comorbidity (congestive heart failure, chronic obstructive pulmonary disease?)	Yes( )	No( )
Are you allergic or did you use misoprostol?	Yes( )	No( )
Do you use an IUD?	Yes( )	No( )
Have you had previous cervical surgery (conization)?	Yes( )	No( )
Is it an ectopic pregnancy?	Yes( )	No( )
Is she in hypovolemic shock?	Yes( )	No( )
Do you have cervical incompetence?	Yes( )	No( )
Does patient have infected abortion (presence of fever, cervical pus, leukocytosis [> 14000])?	Yes( )	No( )
Is it a twin pregnancy?	Yes( )	No( )
Do you have Marfan syndrome?	Yes( )	No( )
Patient with coagulopathy?	Yes( )	No( )

Patient with cervical os opening (4 mm dilation at the time of consultation)?	Yes(  )	No(  )
History of intrauterine manipulation with contaminated objects.	Yes(  )	No(  )

Sign the consent form

Prescribing randomized medication from project 16-0309 WITH

Randomization: Treatment # \_\_\_\_\_, placed at \_\_\_\_:\_\_\_\_\_

INITIATION OF THE PROCEDURE: \_\_\_\_:\_\_\_\_\_

Outcome: adequate dilation for the procedure (  ) Karmann  
cannulas # used:

Dilation NOT suitable for procedure (  ) Hegar  
dilators # used:

Adverse events/observations:

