## **STUDY GOALS**

### **Primary**

To verify if a dose of 200 µg of misoprostol results in a cervical priming is not

less than 25% at the dose of 400 µg usually used.

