## **HYPOTHESIS**

Our null hypothesis is that  $P_{\text{standard (400µg)}} \geq P_{\text{alternative (200µg)}} + 25\%$ ;

Our alternative hypothesis is that  $P_{\text{standard (400µg)}} - 25\% < P_{\text{alternative (200µg)}}$ .

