## **Variables:**

1. The control group (400 µg misoprostol);
2. The experimental group (200 µg misoprostol);
3. Cervical dilation present or not.

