## **Outcomes**

The following outcomes will be determined:

1. Dilatation of the cervix without the need for a dilator between 3 and 6 hours after placing the misoprostol;
2. Dilatation of the cervix with 8mm. The measurement of cervical dilation will be done with a Karmann cannula, starting with the largest diameter (11 mm) and decreasing until it was possible to introduce, without resistance, the cannula into the uterine cavity (continuous variable 4 to 11).

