## **Sample size**

The sample size was calculated as a non-inferiority clinical trial according to the literature (Blackwelder 1982). We expected that cervical dilation would be achieved in 96% of the cases using 400 µg of misoprostol and 86% in the 200 µg group. If there is a true difference in favour of the 400 µg treatment of 10% (96% vs 86%), then at least 184 patients were required in order to be 95% sure that the upper limit of a one-sided 97.5% confidence interval (or equivalently a 95% two-sided confidence interval) would exclude a difference in favour of the standard group of more than 25%.

The determination of non-inferiority margins was based on the literature (Hahn 2012; Wu et al. 2017; Kapp et al. 2010; Singh et al. 1998). It is known that 400 µg of misoprostol yields a 96% cervical dilation > 8 mm (Singh et al. 1998). We considered 86% of the 200 µg misoprostol group as the minimal acceptable percentage. The non-inferiority margin was determined by  $\frac{1}{3}$  of the difference between the 400 µg effect (96.7%), compared to the 200 µg dose (23.3%) found in the literature, i.e.  $73.4 / 3 = 24.46$ . (Fong, Singh, and Prasad 1998; Hahn 2012; Wu et al. 2017; Kapp et al. 2010; Singh et al. 1998).

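### The plan accepts a loss of dilation success up to a 25-point limit, but prespecifies no structured comparison of adverse effects between doses and states no benefit that justifies the margin

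*Combined protocol and SAP*

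**What the plan says.** The primary goal is that priming with 200 µg should be not "less than 25% at the dose of 400 µg usually used", and the Hypothesis section turns this into a 25-point margin on the difference in proportions. The Sample size section assumes that "cervical dilation would be achieved in 96% of the cases using 400 µg of misoprostol and 86% in the 200 µg group", "then at least 184 patients were required", and asks that the upper limit of a two-sided 95% interval exclude a 25-point difference in favour of 400 µg.

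Everything to be compared is dilation. The secondary goal relates dose to degree of dilation. Besides the two dose groups, the Variables section lists only "Cervical dilation present or not". The Outcomes section opens with "The following outcomes will be determined" and gives two items: dilatation without a dilator, and dilatation of 8 mm. The Statistical analysis section deals with dilation and nothing else.

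Adverse effects between doses enter in one place, the last line of the data form: "Adverse events/observations". It has no item list, no yes/no box and no time window. The Introduction mentions adverse effects only when comparing surgical with pharmacological evacuation. Its reason for testing 200 µg is that smaller doses have been studied too little, and the Justification adds that the evidence on efficacy is inconclusive.

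**The concern.** A non-inferiority margin is a price: the loss of efficacy one would accept in return for something else. Here the price is given and the return is not. If the trial succeeds, a reader choosing between doses will know that the loss is probably below 25 points, but the plan promises no figure for what the lower dose offers in exchange.

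The one field that could supply such a figure is weak for the purpose. It is shared with general remarks, and an empty line cannot be read as either absence of symptoms or absence of a question. Counts taken from it by arm would have an uncertain denominator, and mild effects are the ones most likely to go unwritten.

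**Working it through.** **1. The plan's sample size.** Inputs from the Sample size section: 96% and 86%, margin 25 points, one-sided 0.025, 95% power. Equal allocation is assumed from two arms and blocks of four; the ratio is not stated.

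n per arm = (1.960 + 1.645)² × (0.96×0.04 + 0.86×0.14) / (0.25 − 0.10)² = (1.960 + 1.645)² × 0.1588 / 0.0225 = 91.7, rounded up to 92, so 184 in total. The stated figure reproduces exactly, which confirms that 25 points is the operative margin.

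**2. The worst observed result that still passes.** Take 88/92 (95.7%) on 400 µg, the whole number nearest to 96%. With a Wald interval:

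- 74/92 (80.4%) on 200 µg: difference 15.2 points; standard error √(0.957×0.043/92 + 0.804×0.196/92) = 4.65 points; upper limit 15.2 + 1.96×4.65 = 24.3. Passes.
- 73/92 (79.3%): difference 16.3 points; standard error 4.73; upper limit 25.6. Fails.

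An observed deficit of about 15 points can therefore be declared non-inferior.

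**3. What a structured adverse-effect comparison could show with the same patients.** The documents give no event rates, so the rates below are assumptions shown over a range. The test is two-sided at 0.05 with 92 per arm:

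power = Φ{[(p₁ − p₂) − 1.96·SE₀] / SE₁}, where SE₀ = √(2p̄(1 − p̄)/92), p̄ is the mean of p₁ and p₂, and SE₁ = √(p₁(1 − p₁)/92 + p₂(1 − p₂)/92). The half-width of the 95% interval is 1.96·SE₁.

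| Assumed rate, 400 µg vs 200 µg | Half-width (points) | Power for the halving |
|---|---|---|
| 10% vs 5% | 7.6 | 25% |
| 20% vs 10% | 10.2 | 48% |
| 30% vs 15% | 11.9 | 69% |
| 40% vs 20% | 12.9 | 85% |

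Worked line for 30% vs 15%: SE₁ = √(0.30×0.70/92 + 0.15×0.85/92) = 0.0606; p̄ = 0.225, SE₀ = √(2×0.225×0.775/92) = 0.0616; (0.15 − 1.96×0.0616)/0.0606 = 0.48; Φ(0.48) = 0.69, to rounding.

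For common effects the comparison is informative at the planned size. For effects near 10% or rarer it is not.

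**The case against.** The strongest reply is that the trial asks a dose-efficacy question and answers it: 200 µg is under-tested, and the documents never claim that it is better tolerated. The gain may also be material use. The Treatment section gives one tablet in one arm and a double insertion in the other, so that saving is fixed by design and needs no outcome; the Introduction names low cost among misoprostol's merits, and the reference list includes pharmacoeconomic sources. This stands in part. Tolerability is not the only possible gain, and it would be wrong to conclude that a positive result leaves the dose choice without any support. But the protocol does not name cost, or anything else, as the benefit that justifies the margin.

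Two other readings go further than the documents allow:

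- A reader might infer that the trial cannot show any difference in adverse effects. Each form carries a treatment number and an adverse-event line, so events could be tabulated by arm afterwards. What is missing is a prespecified, structured comparison. The form also does not say whether staff ask the patient, so how much goes unrecorded is unknown and no capture rate can be assumed.
- A reader might take the margin to mean that a 25-point loss is expected or would pass if observed. The planned true loss is 10 points, and 25 is what the confidence limit must exclude.

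**Conclusion.** The point holds as a gap in what the trial can conclude about choosing a dose; it is not a flaw in the primary test. An observed deficit of about 15 points could pass (88/92 vs 74/92, upper limit 24.3), with no prespecified, structured estimate of adverse effects by dose beside it and no stated reason why such a loss would be acceptable. The 15-point figure assumes 92 analysed per arm, a 400 µg result close to the planned 96% and a Wald interval. It would be an overstatement to say that a halving of side effects is simply detectable with the planned patients: power is about 69% at 30% vs 15% and exceeds 80% only for more frequent effects, such as 40% vs 20%. All of these rates are assumed. The change should be made because it is cheap and makes the result more useful for the dose choice.

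**What to change.** 1. **Outcomes.** Add a descriptive outcome, compared by assigned dose: patient-reported and observed effects between misoprostol placement and the start of MVA, plus procedure complications. The investigators should fix the item list in advance. The form already records both times that bound the window.
2. **Form.** Add a yes/no box for each item and keep the free-text line for unlisted events. Symptom items should be completed before the cannula measurement by staff who do not know the dose, hence not by the researcher who places the tablets. Procedure complications should be completed after the procedure.
3. **Statistical analysis.** Add a sentence that each between-dose difference will be reported with its 95% interval beside the non-inferiority result, as description and without a claim of significance.
4. **Sample size or Justification.** State which benefit of the lower dose (tolerability, cost or another) justifies a 25-point margin.

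The cost is a slightly longer form and one extra table, with no added patients or visits. The downside is that the comparisons are several, descriptive and uninformative for rare events.
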